- 2% of control group households will receive WRAP despite being allocated to the 'do not receive intervention' trial arm. This is based on trial arm non-compliance from previous children's social care RCT experience.
- 95% of intervention group receive intervention. This is estimated to be high, given that all households have expressed interest in the intervention.
- Upon administration of the endline survey, 5% of carers are untraceable. This is based on previous children's social care RCT experience.
- By the point of the endline survey, 2% of households withdraw consent. This is based on previous children's social care RCT experience.
- For the primary outcome, 5% have implausible or missing values. We anticipate this being low, as we will primarily rely on an online survey for our primary outcome with set response options.
- 20% of carers do not respond to the endline survey. We anticipate that this will be low due to the use of an incentive voucher, social worker engagement in advance of survey distribution, and a schedule of reminder text messages.

Figure 2. Consort diagram showing participants' journey through the pilot RCT of Barnardo's WRAP programme

To randomise we will set up a system where local authorities provide to Coram by email a unique family ID for each family expressing interest (consenting to participate in the

programme and study). Randomisation will be stratified by local authority. This will include fields to enable us to check whether local authorities have applied the eligibility criteria correctly, before we undertake randomisations (box 1).

We anticipate randomising around 178 households using a securely stored spreadsheet pre-populated with randomisation outcomes, and return the outcomes back to local authorities and Barnardo's within 24 hours. We will do this for the stock of families in March 2023, and then on demand as needed for the in-flow of newly eligible families thereafter until early 2024.

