We have made pragmatic choices, aiming to investigate the outcomes set out in the logic model while minimising burden on local authorities and participants, and maximising data quality and completeness. We have chosen to contact families using an online survey at baseline and endline, with carers without valid email addresses sent a copy by post, and reminders sent by email, post and text message as appropriate. The survey will be sent to all carers in the trial. As shown in the table below, we have scheduled prompt text messages for the baseline and endline survey, and reminder text messages for non-responders to the endline survey. We plan to keep the survey open for one month, but may extend this deadline depending on the response rate.

The baseline survey will be sent to carers shortly after families have been randomised. We therefore anticipate that most surveys will be sent in March 2023 as this is when most families will enter the programme i.e. when local authorities share contact details with Barnardo's to invite families to information sessions. However, where families become eligible or interested throughout the trial period, the survey will be sent on a rolling basis following randomisation. The endline survey will be sent in July 2024, once all WRAP Level 1 delivery has ended. This is so that the endline survey can theoretically capture any change, or lack of change, that has occurred by both adults and children/young people attending Level 1 WRAP. We anticipate that capturing outcomes at endline will pose challenges for retention and have therefore made the following plans to boost the response rate:

¹⁶ Bulus M, Dong N, Kelcey B, Spybrook J (2021). *PowerUpR: Power Analysis Tools for Multilevel Randomized Experiments*. R package version 1.1.0, <https://CRAN.R-project.org/package=PowerUpR>.

1. Foster carers and kinship carers will receive a £10 voucher upon completion of the survey at baseline and another £10 voucher at endline.
2. We will send a reminder text and email ahead of the endline survey (June 2024) to remind foster and kinship carers that they will receive the survey in July 2024.
3. We will consider phoning all randomised foster carers and kinship carers at midpoint as a courtesy to check on engagement and remind them of the endline survey. However, we will weigh this up against whether this will be too much contact and considered a nuisance.

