4. We will work with Barnardo's to explore mechanisms for reminding participants of the endline survey, including social media, via fostering social workers, and at the Keeping Connected groups.
5. We will check whether contact details for participants are up-to-date with local authority records.

In order to minimise data storage and use the most up-to-date contact details, we will obtain contact details for all randomised carers from the Barnardo's Expression of Interest form.

Table 3. Milestones for outcome measure collection

Task	Date
Referrals of families sent by Barnardo's to Coram	March-April 2023
Eligible referred families randomised by Coram, then randomisation outcomes shared with local authorities and Barnardo's	March – April 2023
Coram emails/posts baseline survey to carers (with prompt text message, if mobile phone number available)	March – April 2023
Coram randomises eligible referred families, then emails/posts baseline surveys to carers (with prompt text message, if possible)	March 2023 – March 2024
Coram sends endline survey by email/post to carers (with prompt text message, if mobile phone number available)	1 st July 2024
Coram requests administrative data from local authorities	1 st July 2024
Coram sends reminder email/text message/post to non-respondent carers	July 2024
Deadline for local authorities to send Coram administrative data request Deadline for carers to complete endline survey	31 st July 2024

The online baseline and endline surveys are hosted on Smart Survey. The prompt text message will read:

'Hi, we're Coram. You may remember agreeing to take part in our study of families in Hull and Lincolnshire. Today we emailed you a survey about your experiences as a carer: [link]. Please complete by 30th April. We will send you a £10 voucher if you complete this survey, and we will also send you another £10 voucher if you complete an additional survey in July 2024.'

The reminder text for the endline survey will read:

'Last chance to have your say! We have emailed you a survey about your experiences as a carer. Your response will help Barnardo's and local authorities to offer the best possible wellbeing support to the fostering community. We will send you a £10 voucher if you complete this survey by 31st July. The link to the survey is [link]'

We will also consider including an additional prize draw in a reminder text, dependent on the response rate.

Type	Outcome	Outcome measure	Collected from	Baseline	Endline

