[name], Research Assistant	Administrative research support, such as carrying out randomisation and sending text messages
[name], Research Associate	Freelance qualitative planning and analysis input as needed, as a senior researcher

Timeline

Table 6. Project timeline

Dates	Activity	Staff responsible/leading
September - February 2023	Research ethics application and approval, protocol drafting and revisions, discussion with experts and advisers, What Works for Children's Social Care review draft protocol, drafting and finalising data sharing agreements and memorandums of understanding	Coram
March 2023	Protocol publication	Coram
March 2023	Request carer contact details from local authorities, hold information sessions	Barnardo's
March - April 2023	First batch of randomisations	Coram
March 2023 -- March 2024	Randomisation: subsequent waves (on demand)	Coram
20 th March 2023	Baseline survey sent to carers	[name]
31 st April 2023	Deadline for baseline survey	[name]
April-June 2023	WRAP phase 1 delivery (see intervention protocol)	Barnardo's
May 2023	Observation of WRAP groups	[name]
Aug-Oct 2023	WRAP phase 2 delivery (see intervention protocol)	Barnardo's
July-Sept 2023	First batch of interviews with participants, social workers, and Barnardo's staff	[name]
September 2023	Observation of WRAP groups	[name]
July – September 2023	Interviews with children, carers and professionals	[name]
October 2023	Midpoint meeting with evaluation advisors	Coram

November 2023	Interim report	Coram
Dec 2023-Feb 2024	WRAP phase 3 delivery (see intervention protocol)	Barnardo's
January 2024	Observation of WRAP groups	[name]
March-May 2024	Second batch of interviews with participants, social workers, and Barnardo's staff	[name]
April-June 2024	WRAP phase 4 delivery (see intervention protocol for details)	Barnardo's
April-June 2024	Survey of professionals	[name]
1 st July 2024	Endline survey sent to carers	[name]
1 st July 2024	Request admin data from local authorities, request costs from local authorities and Barnardo's	[name]
31 st July 2024	Deadline for endline carer survey	[name]
31 st July 2024	Deadline for administrative data return and costs from local authorities and Barnardo's	[name]
June – September 2024	Analysis, drafting, revisions, meeting of evaluation advisors	Coram

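### The baseline carer survey follows randomisation and release of allocation and can overlap WRAP delivery, so any analysis that uses baseline WEMWBS is open to bias

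*Protocol*

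**What the plan says.** The order of steps is fixed in several places in the Protocol.

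- **Randomisation:** the evaluator will "return the outcomes back to local authorities and Barnardo's within 24 hours".
- **Outcome measures:** "The baseline survey will be sent to carers shortly after families have been randomised". For families who enter later, "the survey will be sent on a rolling basis following randomisation".
- **Table 3:** one row reads "Eligible referred families randomised by Coram, then randomisation outcomes shared with local authorities and Barnardo's"; the row after it is the mailing of the baseline survey.
- **Survey window:** Table 6 dates the mailing 20 March 2023. The prompt text message says "Please complete by 30th April". Outcome measures adds: "We plan to keep the survey open for one month, but may extend this deadline depending on the response rate".
- **Delivery:** Table 6 puts WRAP phase 1 in April to June 2023. Level 1 WRAP delivery says that this phase concentrates on carers and social workers, and that the adult course is three sessions, each a short day.

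Nothing shown withholds allocation until baseline is returned, requires baseline before the first session, or says how late baselines are handled.

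**The concern.** The survey respondents are the carers whose WEMWBS score is the primary outcome, and they are also the first family members to receive WRAP. A self-reported score taken after allocation may already carry pleasure or disappointment at the result. If it is taken in April, it may carry the course itself, which is short enough for a carer to finish before replying. The same applies to the baseline peer-support item, the BAC and the SCORE-15. Willingness to return the baseline survey can also differ by arm.

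Baseline WEMWBS is used in the balance check that decides which covariates enter the primary model (Descriptives; Primary outcome analysis) and in the sensitivity models. It is also used in the compliance analysis of change and, if triggered, in carrying the last observation forward (Treatment of missing data). Adjusting for a variable that allocation has moved removes part of the effect that the trial is meant to estimate. The imbalance rule adds to the problem: a reaction to allocation can itself create the imbalance that brings baseline WEMWBS into the primary model, and the data cannot separate that from chance imbalance.

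**Working it through.** **1. Timing.** The deadline of 30 April is 41 days after the mailing of 20 March, and the last 30 dates of that window lie in April. Up to 30 days can therefore overlap phase 1, before any extension. The start day within April is not given, and most surveys are expected to go out in March, so the share of late responses is unknown.

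**2. The plan's own MDES.** Inputs (sample size table; Annex 2): ICC 0.4, carer-level R² 0.6, family-level R² 0, 1.9 adults per household, 41.3 × 3 = 123.9 households, equal allocation.

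- SE = √[0.4/(0.25 × 123.9) + 0.6 × (1 − 0.6)/(0.25 × 123.9 × 1.9)] = √(0.01291 + 0.00408) = 0.130
- With 117.9 degrees of freedom, MDES = 0.368, against 0.37 stated. The figure reproduces.
- With carer-level R² set to 0 (baseline unusable), SE = 0.152 and MDES = 0.43.

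**3. Slope of endline on baseline.** The Protocol gives no slope, so a range is needed. Assume equal SDs at both times and that all the explained variance comes from baseline.

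- R² 0.6 at carer level only, as coded: total R² = 0.6 × (1 − 0.4) = 0.36, so b = √0.36 = 0.60.
- R² 0.6 read as total: b = √0.6 = 0.775.

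**4. Effect on an adjusted estimate.** If allocation moves the baseline difference by g, the adjusted estimate shifts by −b × g. With an assumed g = 0.1 SD, the shift is 0.060 to 0.078 SD, towards the null if the reaction favours the intervention arm. If a share f of the effect is already present at baseline, the adjusted estimate is the true effect × (1 − b × f). For a true effect of 0.37, with SE held at 0.130 (power 80% without contamination):

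| f (assumed) | Loss | Adjusted estimate | Power |
|---|---|---|---|
| 10% | 6–8% | 0.35–0.34 | 75–74% |
| 25% | 15–19% | 0.31–0.30 | 67–62% |
| 50% | 30–39% | 0.26–0.23 | 50–41% |

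In a simple change score the slope is 1, so the whole of g is subtracted: f = 25% gives 0.37 × 0.75 = 0.28.

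**5. How often the primary model would adjust.** The SE of a baseline difference is √[0.4/(0.25 × H) + 0.6/(0.25 × H × 1.9)] for H households.

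- H = 124: SE = 0.152, 0.1/0.152 = 0.66, chance of two-sided p < 0.05 about 10%.
- H = 178: SE = 0.127, 0.1/0.127 = 0.79, chance about 12%.

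Without contamination the chance is 5%.

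**The case against.** The strongest reply is that the main result is largely protected. Under Primary outcome analysis, the primary model takes only predictors that are significantly unbalanced between arms, and baseline WEMWBS is otherwise a candidate for sensitivity analyses. An endline comparison that does not use baseline is untouched by a contaminated baseline. Carrying observations forward is conditional too, on missingness being related to arm. This stands, and it limits the point to the analyses that use baseline.

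A reader might infer more than the documents support:

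- **That carers know their allocation when they answer.** The Protocol says when local authorities and Barnardo's are told, not when families are. Prior knowledge is likely given the 24-hour release and the April start, but it is an inference.
- **That a known bias of 0.08 SD or 19% enters the primary estimate.** Those are the upper ends of a range, they rest on assumed contamination, and they apply only where baseline is adjusted for.
- **That the balance checks fail altogether.** Carer gender, ethnic group and address come from local authority data at randomisation (Annex 3), not from the survey.
- **That late baselines should be set to missing.** That would delete data almost only in the intervention arm and create missingness by arm through the rule itself.

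The fix also meets fair practical objections. Barnardo's collates the Expression of Interest forms, while Confidentiality and anonymity promises that survey answers are not shared. One carer may consent for the household, so a survey on that form could miss other adults. Recruitment is already rated a high risk. The first two are met by keeping the survey with the evaluator and sending it to each adult; the third remains as a modest cost.

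**Conclusion.** The point holds as a weakness of design, not as a demonstrated bias in the primary result. The Protocol places baseline collection after randomisation and after release of allocation, with a window that can run into delivery to the same carers, and states no safeguard. Analyses that adjust for baseline WEMWBS, use change from it, or carry it forward are exposed; the unadjusted endline comparison is not.

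The size depends on contamination that the documents do not let one estimate. Under the stated assumptions the illustrative figures are 0.06 to 0.08 SD for a 0.1 SD gap, and a 15% to 19% loss if a quarter of the effect is already present. The imbalance rule would carry a 0.1 SD gap into the primary model in about one trial in ten to one in eight. The order of steps should be changed: an analysis plan written later cannot restore a baseline unaffected by allocation, and the pilot is meant to inform a full-scale trial.

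**What to change.** Revise Outcome measures, the 24-hour release under Randomisation, and Tables 3 and 6, so that:

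1. The evaluator sends its own survey link to every consenting adult, using the contact details from the Expression of Interest form, before allocation is released. Responses stay separate from Barnardo's, which keeps the confidentiality promise.
2. Each family's allocation is released only once baseline is returned or a short fixed window closes. The same rule applies to later entrants.
3. For families already informed, the baseline completion date is recorded against the date of allocation notice and the first WRAP session. Annex 3 already collects the dates of randomisation and first session. A sensitivity analysis then examines late baselines, which are kept in the main analysis.

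While editing, reconcile the dates: the baseline deadline is 30 April in the text message but 31 April in Table 6, and the first randomisations are in February 2023 under Procedures but March 2023 under Randomisation.

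The cost is a delay of days in allocation notice and a small added burden at sign-up from a survey timed at about 15 minutes. No new instrument is needed, and a clean baseline leaves the MDES at 0.37.

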delivery of WRAP through peer support groups ('Level 1 WRAP'), the training of facilitators in the fostering and kinship community ('Level 2 WRAP'), and the facilitation of 'Keeping Connected' groups. The Copeland Center is licensed by the non-profit organisation Advocates for Human Potential (owners of the WRAP model) to oversee WRAP co-facilitator training and certification. The Barnardo's delivery team are on course to become a Copeland accredited WRAP Centre of Excellence. The focus of this RCT is the evaluation of Level 1 WRAP, as this is the main basis of the intervention. While Level 2 WRAP and Keeping Connected groups are part of the approach, designed to support and sustain the programme, they will be delivered later in the intervention timeline and are optional. We do not yet have a good idea of how many people will take up these offers, however they will be explored in the IPE if the participant has taken part.

Level 1 WRAP delivery

The Level 1 WRAP intervention will take place in youth and community settings across Hull, North Lincolnshire and North East Lincolnshire, for example, in town halls and council buildings. The intervention will be delivered to foster children, kinship children, birth children, foster carers, kinship carers, other adults in the household (such as partners and relatives), and social workers.

Phase 1 delivery will focus on foster carers, kinship carers and social workers to equip them with resources to understand and support their own wellness, so they are better placed to support foster and kinship families. Barnardo's aim to support 240 adults and 240 children through Level 1 WRAP. WRAP groups for social workers will not be randomised as part of the current impact evaluation. Barnardo's have invited all social workers in the three local authorities to take part in the WRAP intervention ahead of the trial, to aid programme buy-in and referrals.

Wellness Recovery Action Plan (WRAP) will be delivered to participants in the following group sizes:

- Adults: maximum of 16 participants per programme
- Foster and kinship children: maximum of eight participants per programme
- Birth children: maximum of 12 participants per programme.

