Barnardo's will make the three local authorities aware of ongoing support available should this be needed, including access to mentoring support until the end of the programme for WRAP facilitators, access to WRAP-related resources for all fostering and kinship community members and peer support groups for WRAP facilitators. The local authorities will have access to further WRAP Level 2 training courses to extend the pool of trained facilitators as well as Barnardo's workers for future WRAP courses where needed to support any facilitation gaps. Future train the trainer courses and peer-led meetings could also include training some short break carers.

Keeping Connected Groups

Barnardo's staff will support facilitation of Keeping Connected groups which provide participants with opportunities to maintain connections, provide peer support to one another, and promote the continued use of WRAP plans after the WRAP groups have finished.

Barnardo's anticipate the Keeping Connected groups will run monthly for 90 minutes and different groups will be encouraged to mix with other groups to broaden connections and peer-support options. These groups provide participants with opportunities to maintain connections once the Level 1 sessions have ended, and to promote the continued use of WRAP plans. Involvement of Barnardo's staff in facilitation of these groups will reduce gradually over the project period with the aim that the groups will continue without Barnardo's input once the project has ended.

Evidence base

The impact of the Wellness Recovery Action Plan (WRAP) intervention has been widely researched. There have been two systematic syntheses of the international WRAP evidence

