For outcome data, we will compute missingness indicators for each of our outcomes and regress these indicators on covariates. If these are significant, then the data is not missing completely at random. We will also check whether the data is experimentally missing at random by regressing the missingness indicator on a treatment dummy. If this is not significant, we will use listwise deletion of observations without outcome data, but if this is significant we will use a last observation carried forward (LOCF) approach. For questionnaires such as the SDQ and the WEMWBS, we will prioritise the approach to missing data as specified in the measure guidance. For example, the user guide for the WEMWBS advises against imputing missing data for participants where more than three items are missing²¹.

We will use multiple imputation for our covariates and conduct our analyses and compare this with our analysis for only complete cases. We will then assess both outputs to determine how similar the treatment estimates are in terms of their significance and direction (20% range as rule of thumb). If these coefficients are not similar, we can reasonably conclude that these data are missing not at random. For these data, we will carry out multiple imputation for our main analysis, with accompanying sensitivity analysis to evaluate the assumptions used. If these coefficients are similar and covariate coefficients are not significant when regressed onto missingness indicators, we can conclude that these data are missing completely at random. If the coefficients are similar, but the covariate coefficients are significant we can assume that these data are missing at random. For missing covariates (unknown), we will use mean average imputation and report how this affects the results.

Criteria	Treatment estimates are similar for complete cases analysis and multiply imputed analysis	Treatment estimates are not similar for complete cases analysis and multiply imputed analysis
Covariates significant when regressed onto missingness indicators	Missing at random (MAR) Multiple imputation with accompanying sensitivity analysis Impute missing data to fix bias and for power	Missing not at random (MNAR) Multiple imputation with accompanying sensitivity analysis
Covariates not significant when regressed onto missingness indicators	Missing completely at random (MCAR)	Missing not at random (MNAR)

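### One endline reminder channel the protocol proposes to explore, the Keeping Connected groups, would in practice reach only intervention-arm carers who continued with WRAP, and nothing requires equal reminder effort by arm

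*Protocol*

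**What the plan says.** The Outcome measures section of the protocol lists five plans to improve endline response. In item 4 the evaluator undertakes to explore, jointly with the delivery organisation, "mechanisms for reminding participants of the endline survey, including social media, via fostering social workers, and at the Keeping Connected groups". The verb is explore, so no channel in this item is fixed.

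The section on Keeping Connected Groups describes who attends: "These groups provide participants with opportunities to maintain connections once the Level 1 sessions have ended, and to promote the continued use of WRAP plans". The Let's Connect section calls these groups optional and adds: "We do not yet have a good idea of how many people will take up these offers".

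The assumptions under Randomisation give the likely make-up by arm: "95% of intervention group receive intervention" and "2% of control group households will receive WRAP despite being allocated to the 'do not receive intervention' trial arm".

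The fixed reminders do not depend on arm. They are a text and email in June 2024 and a text, email or postal reminder to non-respondents in July 2024. A midpoint call, if made, would go to all randomised carers. The £10 voucher also applies in both arms.

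Under Treatment of missing data the protocol says: "We will also check whether the data is experimentally missing at random by regressing the missingness indicator on a treatment dummy". If the result is not significant, records without an outcome are deleted listwise. If it is significant, the last observation is carried forward.

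**The concern.** Social media and fostering social workers can in principle reach carers in both arms. A reminder at a Keeping Connected group cannot, because controls have no such group. It also works selectively inside the intervention arm, since it reaches carers who attended WRAP and then kept coming. Part of the groups' purpose is to "promote the continued use of WRAP plans after the WRAP groups have finished", so the prompt to complete the survey would come in a setting that promotes the intervention.

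The primary outcome is WEMWBS, self-reported in a survey by carers who know whether they were referred. If extra questionnaires are recovered from one arm only, and from carers who differ from other non-respondents, the comparison of respondents is no longer a fair comparison of the randomised arms. Perceived peer support is plausibly more exposed, because it counts the other local carers a respondent could ask for help, and regular attenders of a carer group may well name more. The protocol has no rule that reminder effort must be equal by arm. A pilot meant to inform a full trial also needs retention figures by arm that its own procedures have not altered.

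**Working it through.** **Scale: the protocol's own detectable effect.** Inputs from Annex 2: ICC 0.4, level-1 R² 0.6, level-2 R² 0, allocation 0.5, 1.9 adults per household, 41.3 households in each of 3 authorities (123.9 in all), power 0.80, two-sided 5%.

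- Variance = 0.4/(0.25 × 123.9) + (0.6 × 0.4)/(0.25 × 123.9 × 1.9) = 0.01291 + 0.00408 = 0.01699, so the standard error is 0.1304.
- Degrees of freedom = 3 × (41.3 − 2) = 117.9, and the multiplier is 1.980 + 0.845 = 2.825.
- MDES = 2.825 × 0.1304 = 0.368, with interval 0.110 to 0.626. The protocol states 0.37 (0.11 to 0.63), so the figure reproduces. It is not in dispute and serves only as a yardstick.

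**Bias from selective recovery.** The protocol gives no response gap and no difference between extra and other respondents, so both are assumed. Let r be the response without the channel, d the extra response in the intervention arm, and g the difference in SD between extra respondents and the rest. The intervention mean then shifts by d/(r + d) × g. With r = 0.75, the response rate given under the sample-size calculation:

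| Gap d | g = 0.25 | g = 0.5 | Share of 0.37 |
|---|---|---|---|
| 5 points | 0.05/0.80 × 0.25 = 0.016 | 0.031 | 4 to 8% |
| 10 points | 0.10/0.85 × 0.25 = 0.029 | 0.059 | 8 to 16% |
| 15 points | 0.15/0.90 × 0.25 = 0.042 | 0.083 | 11 to 23% |

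The Randomisation section gives 20% non-response, which would make r = 0.80. The 5-point row then becomes 0.05/0.85 × 0.25 = 0.015 and 0.05/0.85 × 0.5 = 0.029, so the choice hardly matters.

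**Would the planned missingness test notice?** Approximate the regression of missingness on arm by a two-sided two-proportion test at 5%, with 167 adults per arm: power = Φ[(d − 1.96 × se₀)/se₁], where se₀ is pooled and se₁ unpooled. To allow for clustering, divide 167 by 1 + (1.9 − 1) × 0.4 = 1.36, giving 122.8. This borrows the ICC for wellbeing, because the protocol gives none for response.

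- 5 points (80% v 75%), no clustering: se₀ = 0.0457, se₁ = 0.0456, (0.05 − 0.0896)/0.0456 = −0.87, power 0.19.
- 5 points, with clustering: se₀ = 0.0533, se₁ = 0.0532, (0.05 − 0.1045)/0.0532 = −1.02, power 0.15.
- 10 points: 0.50 to 0.63.
- 15 points: 0.88 to 0.95.

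A 5-point gap would therefore usually go unnoticed and the analysis would proceed on complete cases. A larger gap would often be noticed, and missing outcomes would then be replaced by earlier scores. Neither route removes selection among those who responded.

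**The case against.** A reader might infer that reminders at these groups are scheduled and that the plan itself will produce arm-dependent response. The text does not support that. Item 4 commits only to exploring mechanisms, take-up of the groups is unknown, and every fixed reminder goes to both arms. Nor does the protocol say that delivery staff would give the reminder, and their part in these groups is meant to shrink over time.

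Large gaps are also hard to reach through this channel. Carers who keep attending are likely to respond anyway. Suppose, as an assumption, that 30 to 40% of intervention adults attend and 85% of them would respond without prompting. Converting every remaining attender then adds 0.15 × 30% to 0.15 × 40%, or 4.5 to 6 points; converting half adds about 2 to 3. A 10-point gain would mean converting 40 to 50% of all non-respondents (10 of 25, or 10 of 20). The groups meet monthly and the survey is planned to stay open for one month, so there may be only one meeting in the window. The direction of bias is uncertain too: continued attendance could reflect unmet need rather than satisfaction with WRAP.

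It is equally tempting to say that the channel would trigger the missingness test and so switch the primary outcome to carried-forward scores. At a 5-point gap that happens only 15 to 19% of the time, and the merit of carrying scores forward is a separate question.

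All of this stands, and it limits certainty and size. It does not answer the remaining point: the channel is named, it has no control-arm counterpart, and no rule keeps reminder effort equal.

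**Conclusion.** The point holds as a risk, conditional on the channel being used. Keeping Connected reminders would reach continuing intervention-arm carers and almost no controls, for self-reported outcomes collected by survey. The size is unknown and probably modest: about 0.02 to 0.03 SD on the primary outcome for an assumed 5-point gap and a 0.25 to 0.5 SD difference. Gaps of 10 to 15 points would give up to about 0.08 SD but look hard to reach this way. No size can be put on the effect on perceived peer support. The missingness test is a weak safeguard at the gaps that are plausible. Reporting the characteristics of those lost to follow-up would help reveal a large imbalance but would not prevent one. No sample-size figure changes.

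**What to change.** In item 4 of the plans to boost response, delete the Keeping Connected groups. Add a rule that every endline reminder has the same content, number and timing in both arms. If fostering social workers or social media are used, the message should go to all randomised carers. Report endline response by arm.

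The evaluator obtains contact details for all randomised carers from the Expression of Interest form, so identical contact is feasible. The cost is the loss of one optional channel and possibly a few intervention-arm responses.
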